2 AIM & OBJECTIVES

The aim of this study is to examine patient acceptability, for providing brief research information, whilst self-completing an automated check-in screen prior to any general practice consultation.

Primary objective

The specific objectives of this study fall into two categories; research evaluation and process evaluation. By piloting the use of the automated check-in screen to collect additional research data, the answers to these objectives will then provide feasibility information on the future use of the automated check-in screens for the identification of potentially eligible participants that would be happy to be contacted about future research studies relevant to their health and with information on patient acceptability of answering simple research questions, within the general practice waiting room.

Research evaluation objectives:

1. To examine completion rates of the two additional research questions on the automated check-in screen.
2. To estimate the number of patients that would be happy to be contacted about future research studies relevant to their health.
3. To estimate the number of patients reporting degrees of pain and which severities of pain.
4. To explore any demographic variances in completion responses.
5. To estimate research question completion rate feasibility, for future use of automated check-in screens in the collection of research data.

Process evaluation objectives;

1. To assess patient acceptability of answering an additional two research questions within the waiting room, whilst completing an automated check-in screen.
2. To explore research question completion rates depending on the time differences between; check-in completion, booked appointment time and actual consultation time.
3. To assess the impact of check-in completion for general practice operationalisation.
4. To describe the quantity and detail of any participant queries, made as a result of asking two additional research questions on the patient automated check-in screen.

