5.6 Data collection

A pseudonymised data extraction, for all booked appointments scheduled and attended during the three-week recruitment period at each participating practice, for those patients of age 18 years or older, will be downloaded. Data to be included in the download will include; patient demographic data (gender and age), date and times (of patient check-in, booked appointment and consultation), check-in ID (system user / practice) and self-reported answers to the two research questions. These items will form the basis of the quantitative data collection, see Table 1 for data items and from where the quantitative data will be collected.

For each participating practice, metadata to include; practice list size, demographic data (gender and age), deprivation score and total number of practice based consultations booked over the three-week recruitment period, will also be collected at aggregate level.

Participant data provided in terms of check-in queries, made as a result of the two additional research questions on the patient automated check-in screen will be anonymously logged by practice administration staff, to assess the impact of check-in completion for general practice operationalisation. The log of queries will be populated for a total of 4 weeks. Three weeks, during recruitment to the study and for one week following the end of recruitment.

Automated check-in data collection

Patients will be asked to complete two self-report research questions during automated check-in for a booked appointment at their general practice. The data entered will be appended to their electronic medical record and pseudonymised data will be downloaded, for all patients for whom the research questions appeared. This data will consist of unique study identifiers, gender, age, times (check-in, booked and consultation), check-in ID (system user / practice) and the study research coded entries.

Table 1: Data items and method of data collection

Data items	Description	Method of data collection
Patient demographics	Gender	EMIS data extraction
	Age	
Date and time of:	Check-in	
	Booked appointment	
	Consultation	
Check-in ID	Dichotomous: 'System user' or 'Practice'	Patient self-reported
Degree of bodily pain experienced during the past 4 weeks.	Single question: 1-6 point scale – degree of pain	
Consent to contact about future research studies of relevance.	Dichotomous: Yes or No	

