6 STATISTICS AND DATA ANALYSIS

6.1 Sample size calculation

The average list size of CRN WM general practices is 7,500 patients, of which approximately 6,000 (80%) will be 18 years of age or over. With the minimum required appointments, per week, per 1,000 patients being 72¹¹. Assuming the same rate of appointment use in those under and over 18 years, there will be an average of 432 appointments per week for those aged 18 years of age or over. Over three weeks therefore, discounting an approximate 10% of patients who have either; >1 appointment booked within the three-week period, lack capacity to complete the automated check-in screen, or the appointment is for either a telephone appointment or a home visit, the practices can expect approximately 1166 eligible participants.

One of the outcomes of this study is to estimate the proportion of people who are happy for their practice to contact them about any future research studies which are relevant to their health. Assuming that approximately 50% will respond positively to this question, 9604 people will need to respond to the question in order to estimate a 95% confidence interval for this proportion formally with a precision of 0.01. Assuming that 80% of those who use the automated check-in complete the additional questions, this would require approximately 12005 people to complete an on-screen check-in in order to achieve sufficient responders. This equates to approximately 11 practices displaying the questions for 3 weeks each, dependent on practice size and actual use of the automated check-in screens.

One AC DC participant check-in query log per practice, completed by practice administration staff, with regards to queries made as a result of the two additional research questions on the patient automated check-in screen, will allow the study team to assess the impact of check-in completion for general practice operationalisation.

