6.2 Statistical analysis plan

Simple descriptive statistics will be used to compare any demographic differences between responders and non-responders and to characterise the study sample. This is a descriptive study and we will determine frequencies and percentages of responses to the 2 questions, stratified by age, gender and practice. Mean or median times (as appropriate) between check-in, booked appointment and time of

consultation will be calculated in responders and non-responders separately. In the production of and reporting on subgroups, ONS guidance will be followed on statistical microdata, to ensure the confidentiality of individual persons is protected¹³.

Thematic content analysis will be used to interpret the participant data logged by practice administrative staff.

In accordance with Keele University SOPs, a Statistical Analysis Plan (SAP) will be completed prior to the end of recruitment.

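### Process objective 2 asks for completion rates by time interval, but section 6.2 plans only average times by responder status, which do not yield those rates

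*Combined protocol and SAP*

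**What the plan says.** Section 2 sets process evaluation objective 2 as: "To explore research question completion rates depending on the time differences between; check-in completion, booked appointment time and actual consultation time". The quantity of interest is a completion rate, conditional on an interval.

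Section 5.6 provides the data. The patient-level extract includes "date and times (of patient check-in, booked appointment and consultation", so every interval in the objective can be computed for each patient.

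Section 6.2 plans two kinds of output that could bear on this objective:

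- For the responses, "frequencies and percentages of responses to the 2 questions, stratified by age, gender and practice". Time is not among the strata.
- For timing, one sentence: "Mean or median times (as appropriate) between check-in, booked appointment and time of" ... "consultation will be calculated in responders and non-responders separately".

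Section 6.2 closes by stating that "a Statistical Analysis Plan (SAP) will be completed prior to the end of recruitment". The content of that separate SAP is not part of the document reviewed.

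**The concern.** The objective conditions on time and asks for the rate. The planned analysis conditions on responder status and reports the time. A difference in average interval between responders and non-responders would hint that completion and timing are linked, at least where completion rises or falls steadily with the interval. It would not give completion for any interval, and it can miss a relation that rises and then falls.

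This matters because the study is meant to inform future use of check-in screens. Section 5.2 places the questions before attendance is confirmed, so time pressure on arrival is a plausible reason for not answering. A practice considering the screen would want the share of late, on-time and early arrivals who complete. A reader of the planned output could learn that responders arrived about a minute earlier on average, yet could not say how low completion is among those who arrive late.

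**Working it through.** **The plan's own figures.** Section 6.1 reproduces, and none of it is in dispute.

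- Responders needed: 1.96² × 0.5 × 0.5 / 0.01² = 9604.
- Check-ins needed at 80% completion: 9604 / 0.80 = 12,005.
- Eligible per practice: 6 × 72 × 3 × 0.9 = 1166.4.
- Practices: 12,005 / 1166 = 10.3, rounded up to 11.

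The 80% completion, 12,005 check-ins and 11 practices are used below.

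**Objective against analysis.**

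| | Conditions on | Reports |
|---|---|---|
| Process objective 2 | time interval | completion rate |
| Section 6.2, timing | responder or non-responder | mean or median interval |
| Section 6.2, responses | age, gender, practice | percentage |

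No row of section 6.2 matches the objective, and no other section supplies a rate by interval.

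**Can the planned averages recover the rate?** The documents give no arrival-time distribution, so one is assumed: booked time minus check-in time is normal with mean 7 and SD 6 minutes. Negative values are late arrivals. Overall completion is held at 80%.

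*Pattern A, a step at the booked time.* Assume 65.0% completion in late arrivals.

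- Share late: Φ(−7/6) = 0.1217.
- Completion in the rest: (0.80 − 0.65 × 0.1217) / 0.8783 = 82.1%.
- With φ(7/6) = 0.2020, the mean interval is 7 − 6 × 0.2020 / 0.1217 = −2.96 min in late arrivals and 7 + 6 × 0.2020 / 0.8783 = 8.38 min in the rest.
- Late share among responders: 0.65 × 0.1217 / 0.80 = 0.0989. Responder mean: 0.0989 × (−2.96) + 0.9011 × 8.38 = 7.26 min.
- Late share among non-responders: 0.35 × 0.1217 / 0.20 = 0.2129. Non-responder mean: 0.2129 × (−2.96) + 0.7871 × 8.38 = 5.97 min.

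*Pattern B, a gradual trend.* Let the log-odds of completion rise by 0.0362 per minute, with the intercept set so that overall completion is 80%. Numerical integration gives means of 7.26 and 5.96 to 5.97 min.

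| | Pattern A | Pattern B |
|---|---|---|
| Mean, responders v non-responders (min) | 7.26 v 5.97 | 7.26 v 5.96–5.97 |
| Median, responders v non-responders (min) | 7.19 v 6.13 | 7.26 v 5.96 |
| Completion, late | 65.0% | 73.8% |
| Completion, 0–5 min early | 82.1% | 77.7% |
| Completion, 5–10 min early | 82.1% | 80.5% |
| Completion, more than 10 min early | 82.1% | 83.8% |

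The means agree, but completion in late arrivals differs by 73.8 − 65.0 = 8.8 points. The medians of A and B differ slightly. If the trend is instead tuned to match A's median gap of 1.07 min, completion in late arrivals is 75.0%, still 10 points above A.

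*Pattern C, non-monotone.* Split the same distribution into equal thirds with completion of 73.5%, 93.0% and 73.5%. Overall completion is (73.5 + 93.0 + 73.5) / 3 = 80.0%. By symmetry about 7 minutes, means and medians are 7.0 min in both groups. A contrast of 93.0 − 73.5 = 19.5 points leaves no trace in the planned output.

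**Would a banded table be precise enough?** Take the late band under the assumed distribution, at 65% completion.

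- Size: 0.1217 × 12,005 = 1461 people, about 1461 / 11 = 133 per practice.
- Ignoring practice: 1.96 × √(0.65 × 0.35 / 1461) = ±2.4 points.
- Allowing for practice, with t on 10 df = 2.228 and design effect 1 + (133 − 1) × ICC: an assumed ICC of 0.01 gives a design effect of 2.32 and ±4.2 points; an ICC of 0.05 gives 7.60 and ±7.7 points.

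**The case against.** The strongest reply has four parts.

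1. *The objective is exploratory and the study is a descriptive pilot.* Neither the primary outcome nor the sample size depends on timing, and the planned comparison does bear on whether completion and timing are associated. All of this is true. It limits the priority of the point, but an association in averages is still not the rate that the objective names.
2. *A separate SAP is promised and may contain the table.* It may. What can be said is that the analysis stated in the protocol does not include it, and that nothing is lost if the SAP adds it.
3. *The illustration is constructed.* The arrival distribution, late share, late completion and ICC are all assumed; only the 80% comes from the plan. Measures of spread would also separate the patterns: SDs for responders v non-responders are 5.84 v 6.49 in A, 5.98 v 5.98 in B and 5.77 v 6.86 in C. Section 6.2 names no measure of spread, and adding one would hint at the shape without giving a rate. That two averages cannot fix a rate by interval does not depend on the inputs chosen.
4. *The document does not mention late arrivals, nor say whether the screen accepts a late check-in.* That is fair. The late band is a suggestion about where completion may fall. The gap exists for any choice of bands.

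A simple banded table would by itself meet the objective. The allowance for practice and the rule for repeat display improve that table, but they are refinements and not part of the defect.

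**Conclusion.** The point holds. Followed as written, section 6.2 leaves process objective 2 unanswered, because it reports average times by responder status and no completion rate by time. Under the assumed inputs, the same planned means are compatible with late-arrival completion of 65.0% or 73.8%, and a 19.5-point contrast can vanish entirely. Those sizes rest on the assumed normal distribution (mean 7, SD 6 minutes) and on patterns chosen to show the ambiguity; they are not predictions. The mismatch itself rests only on the wording of sections 2 and 6.2. It should be corrected before analysis. It does not affect the primary outcome, the sample size or the data to be collected.

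**What to change.** Add to section 6.2, or to the SAP still to be completed, a table of completion percentage with 95% CI by bands of booked time minus check-in time. Fix the bands before results are seen and include one for late arrivals.

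- Use each patient's first check-in at which the questions were displayed, so that nobody is counted twice.
- Allow for practice in the CI, with a small-sample correction because there are only about 11 practices.
- Keep the planned mean or median times as supplementary.
- Report the check-in-to-consultation interval descriptively, since the objective names it. Note that the consultation follows the questions, so this interval should not be read as a cause of completion.
- A regression of completion on interval is optional.

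The cost is one extra descriptive table and a short specification of its bands and CI method. The times are already in the section 5.6 extract.

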7 DATA HANDLING

Data management will be carried out in accordance with a Study Data Management Plan, in accordance with Keele University Standard Operating Procedures (SOPs). The study data extracted will contain only pseudonymised data, which will be stored on Keele University servers and password protected. All confidentiality arrangements adhere to relevant data protection regulations and guidelines (General Data Protection Regulation (GDPR), Caldicott, General Medical Council (GMC), Medical Research Council (MRC) UK Policy) and the Chief Investigator and Study Statistician (Data Custodian) have responsibility to ensure the integrity of the data and that all confidentiality procedures are followed. At the end of the study, data will be securely archived in line with the Sponsor's procedures for a minimum of 10 years after publication of the main findings and until the sponsor authorises destruction. Archiving will be carried out in accordance with Keele University SOPs.

Any subsequent requests for access to the data from anyone outside of the research team (e.g. collaboration, joint publication, data sharing requests from publishers) will follow the Keele University SOP data sharing procedure.

8 MONITORING & AUDIT

8.1 Study Management

The study Chief Investigator (CI) is responsible for the conduct of the study and will convene a Study Management Group (SMG) comprising members of the research team. Study management will be carried out in accordance with Keele University SOPs. The SMG will meet at regular intervals throughout the study and will be responsible for the set-up, ongoing management and monitoring and for the interpretation of the results. The SMG will oversee: the protocol completion; obtaining regulatory approval and site set-up; reporting of unexpected events to the REC and Sponsor; monitoring of

screening and recruitment procedures; data collection and software development; completing regulatory reporting requirements.

The CRN WM, will co-ordinate the general practice identification process and co-ordinate local implementation and study set-up for the study team.

8.2 Monitoring arrangements

Study monitoring will be carried out in accordance with a Study Monitoring Plan and Keele University SOPs which lay out the procedures for monitoring the data collection, protocol compliance and data management procedures.

On day 3 of recruitment, an export will be downloaded by general practice administration staff and securely sent to iPCHS via nhs.net email, as a monitoring arrangement to confirm data collection functionality.

8.3 Safety Reporting

No serious or unexpected adverse events are expected as a result of this study.

Data entered with regards to bodily pain experienced over the last 4 weeks will be filed chronologically in the patients' medical record, accessible to the HCP the patient is booked to consult with. The time frame between a patient reporting any bodily pain and being seen by a HCP will be minimal and HCPs will be aware of the study and that the pain score is being collected.

8.4 Study timeline

May 2018 – June 2018:	Finalise study documentation and study technological requirements.
July 2018:	NIHR Clinical Research Network Portfolio adoption. Liaison with general practices. Obtain ethics and regulatory governance approvals.
November 2018 – April 2019:	Recruitment
May 2019 – July 2019:	Data cleaning and data analysis.
From July 2019:	Dissemination

9 ETHICAL AND REGULATORY CONSIDERATIONS

Health Research Authority (HRA) approvals will be applied for and sought before the study commences. HRA Approval is the process for the NHS in England that brings together the assessment of governance and legal compliance, with independent Research Ethics Committee opinion provided through the UK Health Departments' Research Ethics Service.

9.1 Research Ethics Committee (REC) review and reports

The study will be submitted to and approved by a Research Ethics Committee (REC) under proportionate review and the appropriate Site Specific Assessor for each participating site prior to entering participants into the study.

Following initial approval from the REC, the REC will be updated of the study progress in line with Keele University SOPs.

9.2 Patient and Public Involvement and Engagement

In the UK there is a clear policy directive to involve patients and the public in research¹². Such involvement will lead to research that is of greater relevance and of better quality. Keele University have an established Research User Group (RUG) who provide advice and feedback on study/trial conduct and offer patient and public representation on studies.

Patient involvement pre-study (April 2018)

8 patients from Keele's RUG have helped to develop the study in the following ways:

RESEARCH DESIGN:

Question development

Patients have assessed the proposed research questions (and discussed the required patient facing documentation) in terms of content, layout, style, order of questions, and overall length.

Data collection processes

Patients have helped to ensure presentation, content and functionally are acceptable for use within a general practice waiting room.

DISSEMINATION:

Results from the pilot feasibility study will be presented back to the RUG as they are interested in the acceptability of the intervention and would like to be involved in any amendments that are required should the study methodology be rolled out further for future research.

9.3 Regulatory compliance

Before any site can enrol patients into the study, the CI or designee will apply for HRA approval. For any amendment see section 9.7.

9.4 Protocol compliance

All instances of protocol deviations will be assessed for severity by the CI (or their delegate), in accordance with the study protocol and using the Sponsor's GCP and Protocol Deviations FOR25.1 Initial Report.

Both Corrective and Preventative actions should be considered to both correct the deviation and/or prevent the deviation from occurring again.

9.5 Data protection and patient confidentiality

All information collected during the course of the study will be kept strictly confidential. Information will be held securely and managed electronically by Keele University and in accordance with Keele University SOPs.

9.6 Indemnity

This study is sponsored by Keele University and Keele University will be liable for negligent harm caused by the design of the study.

The NHS has a duty of care to patients treated, whether or not the patient is taking part in a clinical research study, and the NHS organisation remains liable for clinical negligence and other negligent harm to patients under this duty of care.

9.7 Amendments

The need for any potential protocol amendment will be raised with the CI and will be discussed with both the SMG and Sponsor prior to being agreed. Updated versions of the protocol will not be circulated for use until the appropriate regulatory parties have approved the amendment, at which point every effort will be made to implement this updated protocol as soon as is practicably possible, superseding the previous version and documenting the date at which the new protocol was implemented.

10 DISSEMINATION

10.1 Dissemination policy

The Research Institute for Primary Care and Health Sciences (iPCHS) has a dedicated infrastructure, linked to strong regional, national and international health care and academic networks, which facilitate dissemination of our research findings to key policy, commissioning clinical, health education and patient stakeholders. The research team will be able to access our dedicated infrastructure to identify and promote research outputs that lend themselves to translation by health providers. Our strong regional partnership with the NHS (formalised through the Primary Care Research Consortium) and our leadership of the Person Centred Care programme of the West Midlands' Academic Health Sciences Network provides further mechanisms to secure effective dissemination of our research findings at national and European levels, through access to the European Innovation and Technology funding streams. The study findings will be published in a peer-reviewed journal and made available via open access.

